#### 3.4 Study Objectives

The proposed research will evaluate the ability of a mobile, rapid induction procedure to engage individuals in ongoing medication assisted treatment. Individuals meeting criteria for opioid use disorder and at high risk of opioid overdose will be enrolled in the study. Recruitment will take place in two targeted neighborhoods with a high prevalence of fatal and non-fatal opioid overdose. A total of 250 participants will be engaged in the research at the time they seek treatment. Following informed consent and determination of eligibility, 125 individuals will be enrolled as they engage with the mobile, rapid induction team and 125 individuals will be enrolled as they seek treatment from the BAC/CRC. All participants will be assessed at 1- and 6-month following enrollment. These assessments will provide data able to address each of the three aims.

- **Aim 1:** To evaluate the impact of the mobile, transitional MAT intervention on its ability to engage participants in targeted, existing MAT treatment slots at 1- and 6-month post-enrollment.
- Aim 2: To evaluate the impact of the mobile intervention on subsequent drug use and overdoses at 6-month postenrollment.
- Aim 3: To assess the acceptability and costs of the intervention. We will document the program and patient costs of delivering and participating in the intervention.

Assessments will also provide data on factors that are considered to be important determinants of retention in treatment—duration of opioid use; prior number of treatment attempts; frequency of recent use; and, depression. In addition to age, gender, and race these variables will be used in the proposed propensity analyses.

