## 3.5 Rationale for Study Design

#### 3.5.1 Why no Randomization?

In the proposed project, individuals will contact our mobile team after learning about the opportunity to begin a rapid induction with buprenorphine/naloxone. As described in more detail later, awareness of the intervention will precede contact with the research team via social media, targeted advertisement, and word of mouth. This is an important feature of the research since we want to be able to measure the acceptability and demand for such a strategy. We believe that it would not be ethical to randomly assign individuals at this point to an alternative treatment option that would require additional time and referral to a different location to initiate screening and intervention. As an "open label" trial, any randomization process would also become widely known among potential participants and contaminate the perception of the mobile team as able to reliably initiate rapid treatment engagement.

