# 5.2 Sample Size and Power Determination

Our power analysis has been based on this primary aim. Our primary hypothesis is that participants who received rapid induction will more likely be engaged in ongoing treatment at 1- and 6-month follow-up than participants who sought treatment at BAC/CRC. We will test this hypothesis at a 5% level of significance. Our principal interest is in the comparison of engagement rates between the mobile intervention and BAC/CRC groups, at months 1 and 6. Preliminary data suggest an engagement rate of about 20-30% in the BAC/CRC group. Assuming a steady loss to attrition that yields 80% completers, and a within-subject correlation of 0.3, the methods of Diggle et al. (Diggle, Heagerty et al. 2002) show that our sample size of 125 in each group yields 80% power for differences of about 15% in engagement rates between the two groups (e.g., 80% power for BAC/CRC: 25% vs. Mobile: 40%, corresponding to a RR=1.6 and an OR=2.0)

**Propensity score model to account for non-randomized allocation:** The participants are not randomly assigned to the mobile rapid induction intervention and BAC/CRC groups, so it is possible that there will be confounding of the group effect with the effects of characteristics of the participants. We will use a propensity score approach (Rosenbaum 2002, Rothman, Greenland et al. 2008) to account for this. We will use a broad range of baseline variables as covariates in a logistic regression model predicting treatment group, including age, race/ethnicity, gender, number of previous overdoses, number of previous treatments for opiate use disorder, type of opioid used, and depression. The model will yield predicted probabilities of BAC/CRC group for all participants (the propensity score), and we will create a five-level ordinal variable based on the quintiles of the propensity score. We will then include this ordinal variable as a stratum variable in our models.

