**Analyses for the primary aim:** i.e. to evaluate the impact of the mobile, transitional MAT intervention on its ability to engage participants in targeted, existing MAT treatment slots at 1- and 6-month post-enrollment. For each of the 1- and 6-month time points, we will classify participants as being engaged/not-engaged (where non-engaged will include dropped out or missing). We will compare the groups on engagement rates at the two time points using a repeated measures logistic regression model, incorporating the propensity score as described above (Diggle, Heagerty et al. 2002). The fixed effects will be binary indicators of treatment group and time point; we will test for a group by time interaction to assess whether the group effect differs at month 1 and month 6. As there are only two time points, we will use an unstructured covariance matrix to accommodate within-participant covariance.

**Analyses for Aim 2:** We will also use a repeated measures model to compare the groups on the ASI drug composite score at months 1 and 6. The model will be similar to that described for the engagement analyses of Aim 1, but with a beta distribution assumed for the response, to accommodate the bounded range (zero to one) of the ASI composite scores. We will compare the groups on the number of overdoses per patient using repeated measures Poisson regression models, if there is sufficient variability in the number of overdoses reported. If a low rate of overdoses causes convergence issues for the Poisson model, we will classify participants as having no overdoses versus at least one, and compare the groups using repeated measures logistic regression models.

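### The Aim 2 ASI model does not name the baseline ASI drug composite as a covariate, although that score is collected at baseline in both non-randomised groups

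*Combined protocol and SAP*

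**What the plan says.** Section 3.5.1 explains that allocation is by self-selection: "individuals will contact our mobile team after learning about the opportunity to begin a rapid induction". Participants in the comparison group are recruited at the assessment and crisis centres (section 4.9.1).

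Section 5.2 handles the resulting confounding with a propensity score. It states: "We will use a broad range of baseline variables as covariates in a logistic regression model predicting treatment group, including age, race/ethnicity, gender", and continues with "number of previous overdoses, number of previous treatments for opiate use disorder, type of opioid used, and depression". Quintiles of the score enter the models as a stratum variable. Section 3.4 also speaks to the propensity score. It lists "duration of opioid use; prior number of treatment attempts; frequency of recent use; and, depression" as determinants of retention and adds: "In addition to age, gender, and race these variables will be used in the proposed propensity analyses".

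For the primary aim, section 5.2 says: "The fixed effects will be binary indicators of treatment group and time point". The propensity stratum and a test of the group-by-time interaction are added. For Aim 2, the plan will "compare the groups on the ASI drug composite score at months 1 and 6", and: "The model will be similar to that described for the engagement analyses of Aim 1", except that the response is taken to follow a beta distribution.

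The drug section of the ASI is administered at baseline, month 1 and month 6 (section 3.7), and the comparison group completes the same assessments (section 4.9.1). Section 3.8.2 and the Study Summary word this endpoint as the change in substance use and severity of addiction.

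**The concern.** Read as written, the ASI model contains group, time, their interaction (as a test) and the propensity stratum. The baseline value of the outcome is not named there or in either propensity list. The other Aim 2 outcome, overdoses, does have a baseline counterpart in the section 5.2 list (previous overdoses).

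If the two self-selected groups start at different severity, and the stratum does not fully absorb the difference, part of it carries through to months 1 and 6 and is read as a treatment effect. The direction is unknown. Even with no baseline difference, leaving out a measured predictor of the outcome gives up precision. What is at stake is how a secondary comparison is interpreted. The study is powered on treatment engagement (sections 3.7 and 5.2), not on the ASI.

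**Working it through.** **Step 1. Where baseline ASI could enter.**
- Propensity list, section 3.4: age, gender, race, duration of use, previous treatment attempts, frequency of recent use, depression. Baseline ASI is not named.
- Propensity list, section 5.2: age, race/ethnicity, gender, previous overdoses, previous treatments, type of opioid, depression. Baseline ASI is not named, but the list is open-ended.
- ASI outcome model, section 5.2: group, time, interaction test, propensity stratum. Baseline ASI is not named. The open-ended wording describes the propensity model, so it does not supply covariates to this model.

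**Step 2. The plan's own figure.** Section 5.2 gives 125 per arm, 80% completers, engagement of 25% versus 40%, within-subject correlation 0.3, two time points, 5% level (two-sided assumed) and 80% power. The repeated-binary formula is

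n = [1.960 √(2 × 0.325 × 0.675) + 0.842 √(0.25 × 0.75 + 0.40 × 0.60)]² × (1 + 0.3) / (2 × 0.15²) = 98.7 completers per arm,

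and 98.7 / 0.8 = 123.4, against 125 stated. With 100 completers per arm the power is 80.5%. The stated figure reproduces. It concerns Aim 1 and is not disputed. It supplies the 125 × 0.8 = 100 completers per arm used below.

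**Step 3. Bias in the ASI comparison.** Take SD units, a normal approximation to the beta model, and no true effect. Let d be the baseline ASI difference left after the propensity stratum, and r the baseline-to-follow-up correlation. The expected spurious difference is r × d. The documents give neither d nor r. Assumed ranges:
- d = 0.2, r = 0.3: 0.3 × 0.2 = 0.06 SD
- d = 0.4, r = 0.6: 0.6 × 0.4 = 0.24 SD
- d = 0: no bias

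These values treat 0.2 to 0.4 SD as surviving the stratum in full, which means no correlation between baseline ASI and the adjusted covariates. They are therefore an upper range for those inputs.

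**Step 4. How correlation with the covariates shrinks it.** Take a raw baseline ASI difference of 0.4 SD and r = 0.6. Suppose frequency of recent use also differs by 0.4 SD and correlates 0.5 with baseline ASI. By linear approximation, d = 0.4 − 0.5 × 0.4 = 0.20, and the spurious difference is 0.6 × 0.20 = 0.12 SD. If a second, independent covariate differs by 0.25 SD and also correlates 0.5, then d = 0.20 − 0.5 × 0.25 = 0.075, and 0.6 × 0.075 = 0.045 SD. Quintile strata remove somewhat less than linear adjustment. All these inputs are assumptions.

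**Step 5. Precision.** For one visit, 100 completers per arm, two-sided 5% and 80% power:
- without baseline ASI: (1.960 + 0.842) × √(2/100) = 0.396 SD
- with baseline ASI, r = 0.3: 0.396 × √(1 − 0.09) = 0.378 SD
- with baseline ASI, r = 0.6: 0.396 × √(1 − 0.36) = 0.317 SD

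Section 3.7 instead anticipates 90% follow-up at month 6, or 112.5 per arm. The first value is then 2.802 × √(2/112.5) = 0.374 SD, and the proportional gain is the same.

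For scale, 0.06 to 0.24 SD is 0.06/0.396 = 15% to 0.24/0.396 = 61% of the unadjusted detectable difference.

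**The case against.** The strongest reply is that the documents already leave room for this. The section 5.2 propensity list is open-ended, the ASI model is only said to resemble the Aim 1 model, and the endpoint is worded as change, so an analyst could include baseline ASI without departing from the plan. That stands in part: the right description is that the covariate is not specified, and a reader should not infer that it will be left out. Nor is Aim 2 unadjusted, since the propensity stratum applies to it. But an open propensity list does not put the baseline value into the outcome model, and putting it only into the propensity score passes it through five coarse strata.

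The second reply is that the covariates the plan does commit to, especially frequency and duration of use, probably share information with the ASI drug score. That also stands, and Step 4 shows that it can reduce the bias a great deal. It does not restore the lost precision in full.

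A reader might go further and infer that the two propensity lists conflict, that duration and frequency of use will be dropped, and that the primary analysis is biased as a result. The documents do not support this. Section 3.4 says that both variables will be used, the section 5.2 wording does not exclude them, and the protocol binds the study to the whole document. The union of the lists is the natural reading. Previous overdoses and type of opioid appear only in section 5.2, which shows that each list is incomplete, not that they contradict each other. The documents also give no ground for claiming that adding baseline ASI would improve the Aim 1 comparison.

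**Conclusion.** The point holds as a free improvement to a secondary analysis. The Aim 2 ASI model compares self-selected groups at months 1 and 6 without naming the baseline value of the same score, which is collected in both groups and which an endpoint worded as change calls for.

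The size of the bias cannot be derived from the documents, and its direction is unknown. The 0.06 to 0.24 SD is an assumption-based upper range. It rests on 0.2 to 0.4 SD of baseline difference surviving the stratum, a correlation of 0.3 to 0.6, and no correlation between baseline ASI and the adjusted covariates. The gain in precision does not depend on any imbalance: the detectable difference falls by about 5% (0.396 to 0.378 SD) at r = 0.3 and 20% (0.396 to 0.317 SD) at r = 0.6. No stated figure in section 5.2 is wrong, and the sample size and the power for the primary aim are unaffected. Adjustment for baseline ASI would not remove confounding by factors that are not measured.

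**What to change.** In section 5.2, under the Aim 2 analyses, state before outcome data are analysed that the baseline ASI drug composite is a covariate in the repeated measures beta model, alongside group, time and the propensity stratum. A covariate suits this model better than a change score as the response: a change score can be negative, which the planned beta distribution on zero to one does not allow.

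The cost is one model term and one sentence. No new data, visits or participants are needed.

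As an editorial change only, cross-reference the propensity lists in sections 3.4 and 5.2 so that their union is used: age, race/ethnicity, gender, previous overdoses, previous treatments, type of opioid, depression, duration of use and frequency of recent use. Adding baseline ASI to the propensity model as well is optional.

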	case manager and PRS will work with the participants to belo them become engaged					
	in existing medication assisted treatment programs					
	• The type of ongoing treatment will be determined on an individual basis and will					
	include options of methadone maintenance, buprenorphine/naloxone treatment, or					
	extended-release naltrexone (XR-NTX).					
	Comparison on engagement rates in ongoing opiate use disorder treatment at the					
	two time points (1- and 6-months) using a repeated measures logistic regression					
	model, incorporating the propensity score (to correct for non-randomized trial)					
	Evaluate the change in substance use and severity of addiction using a repeated					
	measures model to compare the groups on the ASI drug composite score at months					
	1 and 6.					
Statistical	Compare of the number of overdoses per participant between groups using repeated					
Mothodology	measures Poisson regression models, if there is sufficient variability in the number of					
wethodology	Poisson model, we will classify participants as baying no overdoses versus at least					
	one and compare the groups using repeated measures logistic regression models					
	
 
Evaluation of the sensitivity of our main analyses to the presence of missing data by
 
					
	performing a sensitivity analysis, in which we will obtain estimates of the group effect					
	under various non-ignorability assumptions, using selection models to examine the					
	effects of missing data, using logistic regression models, and incorporate the					
	predicted probabilities into a weighted analysis of the main hypotheses.					
	The study will be monitored by the PIs and co-investigators, and Philadelphia Department					
Data and Safat	of Public Health Institutional Review Board, as well as by regulatory committees at the					
Data and Salety	University of Pennsylvania (i.e., IRBs, OHR) and Center for Studies of Addiction Data Safety					
Monitoring Plan	Monitoring Board (Penn DSMB). During the course of the study, safety and data quality					
	monitoring will be performed on an ongoing basis by the Principal Investigator and the study					
	staff.					

The information that follows constitutes the research protocol for the Rapid initiation of buprenorphine/naloxone to

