  - Socio-demographic Questionnaire: This brief questionnaire will be administered by research staff and will collect demographic information (e.g. age, gender, race and ethnic identity, marital status, sexual orientation, educational level, employment status, income and income sources) and descriptive information about the subject's living situation and housing stability, history of involvement with the criminal justice system, drug use, and drug treatment history.

- Addiction Severity Index (ASI) sections for Drugs and Alcohol and Medical Status: The ASI is a structured interview developed to assess the range of problems seen in drug users. The ASI produces severity ratings and composite scores in each of seven areas, and each type score has been assessed with regard to validity and reliability. Severity ratings and composite scores have demonstrated high levels of inter-rater, test-retest, and concurrent reliability (Cacciola et al., 2008; McLellan, Cacciola, Alterman, Rikoon, & Carise, 2006; McLellan et al., 1992). The Medical and the Drug and Alcohol sections will be administered at baseline, 1- and 6-month follow-ups.
- Patient Health Questionnaire (PHQ-9): Given the important role of depression in accessing and adhering to treatments for substance use disorder and other chronic medical problems (Mahajan, Avasthi, Grover, & Chawla, 2014; Tavakkoli, Ferrando, Rabkin, Marks, & Talal, 2013), we will also assess severity of depression using the 9-item Patient Health Questionnaire (PHQ-9). This brief assessment asks participants to indicate the frequency of occurrence of each of the nine DSM-IV diagnostic criteria for depression during the previous two weeks. This instrument has been widely used in clinical research and has strong psychometric properties. The PHQ-9 will be completed at baseline and months 1 and 6.
- Urine drug screen: We will use the CLIA waived® ACON Dip-and-Read 8-panel test for THC, cocaine, opiates, amphetamines, PCP, methamphetamine, benzodiazepines, barbiturates, and buprenorphine. The urine sample will be provided using standard procedures with temperature monitoring to preclude tampering and dilution.

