# 3.8.2 Secondary Study Endpoints

- Evaluate the impact on the number of overdose and evaluate the change in substance use and severity of addiction using a repeated measures model to compare the groups on the ASI drug composite score at months 1 and 6.
- Cost evaluation: We will determine the economic value of the mobile intervention relative to treatment as usual from the perspective of the City of Philadelphia's Department of Public Health. [name], a Health Economist in the HIV Prevention Research Division, Department of Psychiatry, Perelman School of Medicine at the University of Pennsylvania, will lead this portion of study activities with consultations with colleagues at the Center for Health Economics of Treatment Interventions for Substance Use Disorder, HCV, and HIV (CHERISH). The results of this analysis will inform future policy decisions regarding implementation of this novel, mobile strategy for rapid initiation of MAT as a method for engagement in long-term evidence-based treatment. If the intervention in this study shows positive economic value, the City of Philadelphia's Department of Public Health may scale-up the intervention to reach more people throughout the city that may be at risk of opioid overdose. Enhanced interventions may require a greater amount of resources than alternative methods of more basic interventions or the usual standard of care. However, resource-intensive interventions may be justified through the achievement of better outcomes resulting from administering enhanced procedures.

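### The Aim 2 ASI model states no role for baseline ASI, so a severity gap between self-selected groups can carry into this secondary contrast

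*Combined protocol and SAP*

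**What the plan says.** Section 5, *Analyses for Aim 2*, sets the comparison: "We will also use a repeated measures model to compare the groups on the ASI drug composite score at months 1 and 6". It defines the model by reference: "The model will be similar to that described for the engagement analyses of Aim 1, but with a beta distribution assumed for the response". The Aim 1 paragraph supplies the terms: "The fixed effects will be binary indicators of treatment group and time point". It adds a group-by-time test, the propensity stratum, and an unstructured covariance justified by there being only two time points, so baseline ASI is not a response either.

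Section 3.7 schedules the instrument at all three visits: "The Medical and the Drug and Alcohol sections will be administered at baseline, 1- and 6-month follow-ups". The *Comparison group* text in 4.9.1 gives the treatment-as-usual group the same assessments.

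Confounding control is the propensity score in 5.2: "We will use a broad range of baseline variables as covariates in a logistic regression model predicting treatment group". The named variables are age, race/ethnicity, gender and "number of previous overdoses, number of previous treatments for opiate use disorder, type of opioid used, and depression". Section 3.4 also commits duration of opioid use and frequency of recent use to the propensity analyses. Neither list names the ASI composite.

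Section 3.8.2 words the endpoint loosely as change: "evaluate the change in substance use and severity of addiction using a repeated measures model to compare the groups". The Study Summary does the same. Aim 2 itself, in the Summary and 3.4, asks about later drug use and overdose at six months, which is a follow-up level.

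**The concern.** Borrowing the Aim 1 model drops something that Aim 1 did not need. Section 4.4 excludes anyone currently in medication-assisted treatment, so engagement has no baseline variation to adjust for. ASI severity does vary at entry: eligibility in 3.7 requires an opioid use disorder score of at least 4, but scores run to 11.

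The groups also arrive by different routes. Mobile participants contact the team after an awareness campaign; comparators are enrolled at assessment and crisis centres. Section 5.2 itself accepts that confounding is possible. If the groups differ in baseline severity beyond what the strata capture, part of that difference reappears at months 1 and 6 as an apparent effect, or hides a real one. With no gap there is no bias, only some loss of precision.

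**Working it through.** **The plan's own figure.** The documents give no power, SD, baseline gap or correlation for ASI. The one figure available is engagement power. With 25% vs 40%, two visits, correlation 0.3 and two-sided 5%:

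n = [1.96√(2 × 0.325 × 0.675 × 1.3) + 0.842√(1.3 × (0.1875 + 0.24))]² / (2 × 0.15²) = 98.7, so 99 per group.

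Dividing by 0.80 gives 124, against the stated 125; power with 100 completers per group is 80.5%. That figure reproduces and is not in dispute.

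**Inputs for ASI.**
- n = 112 per group, from 90% of 125 (month-6 follow-up in 3.7).
- *Assumed:* d = 0.3, the baseline ASI gap in within-group SD before stratification.
- *Assumed:* ρ = 0.3 to 0.8, the correlation of the propensity covariates with baseline ASI. If 3.4's frequency and duration of use are included, the upper end may be nearer.
- *Assumed:* r = 0.2 to 0.7, the correlation of baseline with follow-up ASI.
- *Assumed:* correlation 0.5 between the two follow-ups, so their mean has variance (1 + 0.5)/2 = 0.75.
- No true treatment effect.

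**Step 1. Gap acts through baseline ASI.** Approximate bias without the baseline term is r·d·(1 − ρ²). For r = 0.5:
- ρ = 0.8: 0.5 × 0.3 × 0.36 = 0.054 SD
- ρ = 0.3: 0.5 × 0.3 × 0.91 = 0.137 SD

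Simulation with quintile strata gives 0.064 and 0.137 SD. The small excess at ρ = 0.8 is plausibly the coarseness of quintiles.

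**Step 2. False positives.** SE ≈ √[2(0.75 − r²ρ²)/112]. For r = 0.5, ρ = 0.3: √(2 × 0.7275/112) = 0.114, so the bias is 0.137/0.114 = 1.20 SE. The rejection rate is Φ(1.20 − 1.96) + Φ(−1.20 − 1.96) ≈ 22%. Simulated ranges over ρ = 0.3 to 0.8:

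| r | Without baseline ASI | With it | Variance cut |
|---|---|---|---|
| 0.2 | 6-8% | about 5% | 0-3% |
| 0.3 | 6-12% | about 5% | 2-7% |
| 0.5 | 8-24% | about 5% | 14-34% |
| 0.7 | 15-39% | about 5% | 45-63% |

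All entries are approximate. At r = 0.3 the closed form r²(1 − ρ²)/(0.75 − r²ρ²) gives a variance cut of 5-11%, because it ignores the collinearity of baseline ASI with group. The gain is modest either way.

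**Step 3. Smaller gaps (r = 0.5).** False positives without the term are 7-13% at 0.2 SD, 5-7% at 0.1 SD and about 5% at zero.

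**Step 4. Beta response.** Beta regression on two stacked visits, with an assumed mean of 0.25 and SD of 0.10, at d = 0.3 and r = 0.5 gives 10-22% without and 5-6% with. The normal outcome is not driving the result.

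**Step 5. Gap that persists in full (r = 0.5, d = 0.3).** Without the term the bias is d − r·d·ρ²: 0.3 − 0.096 = 0.204 to 0.3 − 0.0135 = 0.287 SD (simulated 0.21-0.29). With it, d(1 − r) = 0.15 SD. False positives fall from 52-71% to 34%.

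**Step 6. Change score instead (r = 0.5, d = 0.3, linear model).**
- Gap through baseline ASI: bias (r − 1)·d·(1 − ρ²), simulated −0.06 to −0.14 SD; false positives 9-22%, against about 5% with the covariate.
- Gap persisting in full: bias d·ρ²·(1 − r), simulated +0.09 to +0.01 SD; false positives 5-13%, against 34% with the covariate.

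The ranking reverses, so neither approach is unbiased in both cases. The covariate improves on the stated model in both.

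**The case against.** The strongest reply is that the plan does not shut baseline ASI out. The Aim 2 model is only described as similar to Aim 1, the propensity list is open-ended, and 3.4 commits to severity proxies. Shared eligibility and concurrent recruitment in the same two areas also limit a gap. All of that stands, and it is why the point is that no role is *stated*. A reader might infer that the plan rules baseline ASI out; the text does not say so. Equally, nothing commits the plan to using it.

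A reader might also infer that the endpoint is change and the model therefore fails to estimate it. That is too strong. Aim 2 is phrased as a follow-up outcome, and the sentences that mention change name months 1 and 6 as the comparison and never say change from baseline. This is loose wording.

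Nor do the propensity lists in 3.4 and 5.2 contradict each other: 5.2 is open and 3.4 adds to it, so both can be followed. Aligning them would be tidying and is not part of this point.

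Finally, the sizes rest on assumed inputs, and the largest need a 0.3 SD gap that persists in full. That is correct. The documents contain no evidence that the groups differ in ASI.

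**Conclusion.** The omission is clear from the text; its consequence is conditional. If a baseline severity gap remains after stratification, it can bias the ASI contrast in either direction. For a 0.3 SD gap acting through baseline ASI, the false-positive rate could be barely above 5% or as high as 39%, depending mainly on two correlations that the documents do not give. The covariate restores about 5% in that case and only halves the bias, roughly, if the gap persists in full: from 0.21-0.29 to 0.15 SD at correlation 0.5. The precision gain runs from negligible to large over the same range.

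The documents support adjustment over the model as stated. They do not establish that adjustment is less biased than a change score. The point should be acted on, but it concerns one secondary endpoint. It should not be read as a criticism of the engagement analysis.

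**What to change.** In *Analyses for Aim 2*, write out the ASI model in place of the cross-reference: fixed effects for group, time point, group by time, the propensity stratum and the baseline ASI drug composite. Describe the estimate as the baseline-adjusted group difference in ASI at months 1 and 6, use that description in the Study Summary and 3.8.2, and do not claim that it removes all confounding.

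Prespecify a change-from-baseline comparison as a sensitivity analysis, fitted with a linear model because a change score can be negative and so falls outside the beta range. If the two analyses disagree, report both.

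The cost is one model term, one sensitivity analysis and a few lines of text. No new data are needed, since the baseline ASI is already scheduled for every participant.
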